1.0 Protocol Summary/Synopsis

Title: Michigan ENdoluminal Distraction Device (MENDD) Tolerance Assessment Study

Study Description: We hypothesize the radial and longitudinal forces necessary to produce enterogenesis will cause low levels of discomfort in healthy adult patients. Approved devices will be utilized in an off-label manner to reproduce forces similar to our novel medical device which is designed to treat short bowel syndrome.

Objectives: The primary objective is to assess the discomfort level caused by balloon deployment (radial stretch) within the intestinal lumen in awake patients. Secondary objectives include assessment of the discomfort level caused by producing short term longitudinal stress on the intestinal lumen.

Endpoints: Primary Endpoint: Completion of a pain rating scale during radial stretch. If tolerable pain thresholds are met, subjects will move on to the secondary objectives.

Secondary Endpoints: Completion of a pain rating scale while enduring longitudinal stress on the small bowel.

Study Population: Five otherwise healthy adult patients with small bowel stomas undergoing routine procedures at the University of Michigan will be recruited

Phase: Early Feasibility

Description of Sites/Facilities Enrolling Participants: All individuals will be enrolled at Michigan Medicine.

Description of Study Intervention: The Michigan ENdoluminal Distraction Device (MENDD) centers around the well-known principle of mechano-transduction. This is defined as the conversion of mechanical stimuli to biochemical signals that elicit specific cellular response. In this case, intraluminal, longitudinal tensile forces result in intestinal growth and lengthening (enterogenesis). This study will utilize approved devices in an off-label manner to create forces required to induce intestinal lengthening.

Radial and longitudinal forces are both required, and two devices will be used to create forces in order to test tolerability of a said forces. This is to provide evidence that humans could tolerate the forces produced by a proposed commercially built device.

Study Duration: 6-12 months

Participant Duration: Subjects will be in the study for 15-60 minutes on the day of procedure and monitored per normal recovery under nursing care from their scheduled procedure. Phone interviews will take place at 30 days post procedure to monitor for adverse events.

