3.0 Objectives and Endpoints

The primary objective is to assess the discomfort level in awake patients with radial distension of the intestine to a known diameter. This will be accomplished with deployment of a balloon with similar characteristics to a proposed medical device. The secondary objective is to place longitudinal forces on intestine using a DBE and asses the discomfort level. Longitudinal tension is necessary to create the mechanotransductive forces necessary to induce intestinal growth. However, in this current study, the forces will not be of the duration to induce growth. These studies serve as precursor studies to obtain data on the tolerability of forces placed on bowel during proposed MENDD therapy. Future studies would include placement of a MENDD prototype device in healthy adult volunteers with ileostomies with the objectives to include 1) to demonstrate feasibility of endoscopic placement of MENDD via an existing stoma and 2) to demonstrate no serious adverse events with actuation of the device while in human intestine.

Discomfort levels will be assessed through an interview process

performed by the study team members during the procedures described. Simple validated pain scales and surveys will be used (Figure). The observation period of the study will end either with conclusion of the questionnaire of discomfort described as too great to continue.

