6.0 Study Intervention**6.1 Study Intervention Administration**

In this study, we will use two FDA approved devices in an off-label manner to replicate forces generated by the MENDD device. To test radial stretch of the small bowel, Coda® Balloon Catheters (K032869) will be introduced into the volunteers' intestine over a guide wire. The guide wire (TERUMO Radifocus Glidewire Angled Stiff Shaft .035" x 180cm (X) GS3508, K152740) is used routinely in the gastrointestinal tract as well as endovascularly and will be advanced under endoscopy and fluoroscopy. Coda® Balloons are intended for temporary occlusion of large blood vessels, or to expand vascular prostheses. Because of the primary indications, the balloon diameter must be extremely precise and accurate. A Coda® balloon with a similar diameter and length, compared to our MENDD design, will be used in the first portion of the study. Pain questionnaires will be administered to the subjects in real time. Due to the subjectivity of pain, the pain scales must be completed at the time and cannot be completed after the procedure is over. The balloon will be inflated for 1-2 minutes. If pain is severe, the balloon will be deflated immediately. The balloon will be repositioned and attempted once more

for the duration of 1-2 minutes.

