Volunteers who tolerate the radial stretch will move on to the second portion of the study. The Coda will be removed, and a Double Balloon Endoscope (DBE) (©FUJIFILM Healthcare, K183032) will be introduced retrograde into the stoma. An advanced endoscopist with specific training and credentialling will perform the endoscopic procedure. Typically, this procedure is done antegrade through the oropharynx in an anesthetized individual. In short, the DBE is an endoscope that has a balloon on the scope itself and on an overtube. The scope is advanced through the small bowel by alternately inflating and deflating balloons and bringing the small bowel to the endoscopist by pleating the bowel over the overtube, similar to pulling a curtain over a rod. Our procedure will deviate from the described use. In this study, the DBE will be introduced retrograde through the ileostomy and the inter-balloon distance will be increased causing stretch on the intestine instead of decreased causing the intestinal pleats. As this is a common unintentional consequence of the DBE procedure, safety precautions and alarms have been implemented to prevent damage to the intestine. The device will be left with balloons inflated on tension for 30-60 seconds or until the device turns off due to safety measures built into the device.

Visual Analog Scale Pain Scoring will be used to assess the participants sensation during both parts of the study. Because pain tolerance differs for all people, we will not set pre-determined score in which the procedure will be stopped, but rather rely on the participant and their willingness to continue. The trial will be discontinued if three participants do not tolerate the first stage of this study i.e., the Coda balloons. Pain during the second portion of the protocol (DBE) will not result the termination of the study. The dissimilar characteristics of the DBE balloons with the MENDD prototype balloons are the reason the Coda balloons are used in the first portion of the study and discomfort from the DBE will be noted, but in itself will not be considered a failure of the study.

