The VAS will be used at several timepoints beginning with immediately after insertion of the catheter and prior to balloon expansion. Next the score will be assessed after the balloon is inflated to a known diameter. Should the subject move to the second phase of the study, the VAS will be given after insertion of the DBE prior to deployment of balloons, after deployment of each balloon and during the extension procedure.

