8.0 Adverse Events

8.1 Adverse Events and other reportable events

Any adverse event reported or observed by the participant will be reported per standard IRB reporting. Adverse event means any untoward medical occurrence associated with the use of an intervention in humans, whether or not considered intervention related. Adverse events will be recorded from the time the consent is obtained until the final procedure is complete including completion of VAS and the 30 day follow up phone call. Other reportable information will be reported to the IRB according to standard reporting procedures.

Expected possible adverse events include:

- Damage to the intestinal wall ranging from mild mucosal irritation to full thickness injury or perforation.
- Damage to the stoma
- Bleeding from the intestinal lumen is usually self-limited and will resolve with observation. However, severe damage may require endoscopic or surgical evaluation and/or intervention to obtain hemostasis or repair perforation.
- Discomfort or pain
- Radiation-related risks associated with fluoroscopy include: radiation-induced injuries to the skin and underlying tissues ("burns"), which occur shortly after the exposure, and. radiation-induced cancers

9.0 Statistical Considerations:

9.1 Proposed sample size (number of records to be reviewed):

5 subjects will be enrolled. If 3 fail to complete the radial stretch test with Coda balloon, the study will be terminated.

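### No pain score is scheduled when a Coda inflation is stopped for severe pain, so the primary pain data can miss or understate the worst discomfort

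*Protocol*

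**What the plan says.** The synopsis defines the main outcome as "Primary Endpoint: Completion of a pain rating scale during radial stretch", and the hypothesis there is that discomfort will be low.

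Section 6.1 gives the Coda stage two VAS time points. The first precedes any stretch: "The VAS will be used at several timepoints beginning with immediately after insertion of the catheter and prior to balloon expansion". The second is the only one under stretch: "Next the score will be assessed after the balloon is inflated to a known diameter".

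The planned inflation lasts 1-2 minutes. Section 6.1 adds: "If pain is severe, the balloon will be deflated immediately. The balloon will be repositioned and attempted once more", again for 1-2 minutes. Scoring is in real time, and "the pain scales must be completed at the time and cannot be completed after the procedure is over". No VAS value triggers a stop; the participant's willingness decides.

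Section 3.0 states: "The observation period of the study will end either with conclusion of the questionnaire of discomfort described as too great to continue". This makes sense only if the second "of" is read as "or".

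Two places count participants who do not get through the stage. Section 6.1: "The trial will be discontinued if three participants do not tolerate the first stage of this study i.e., the Coda balloons". Section 9.1, with five participants: "If 3 fail to complete the radial stretch test with Coda balloon, the study will be terminated".

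**The concern.** The study asks how much pain radial stretch causes. The most informative inflation is one so painful that it has to be stopped, yet the schedule ties no rating to that event. Whether the score is lost or taken too early depends on the pain itself, so the error runs one way: recorded pain is too low. With five participants, one or two such inflations can change the picture that section 2.2 wants to use as grounds for commercial manufacture.

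A second, smaller gap concerns the count. The protocol does not say what a stopped first inflation followed by a held second one means for tolerance of the stage.

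**Working it through.** **What the schedule yields.** There are four courses an inflation can take.

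1. Reaches the diameter, is scored and held: scored as planned.
2. Reaches the diameter, is scored, then stopped during the hold: a score exists, but it may precede the pain that ended the inflation.
3. Reaches the diameter, but is stopped before the scale is given: no score under stretch.
4. Stopped on the way up: the scheduled point never occurs, so no score under stretch.

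Courses 2 to 4 follow from the immediate-deflation instruction, and in none of them is a rating tied to the stop. In the double balloon enteroscope stage, by contrast, section 6.1 does schedule a rating during the extension itself.

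**Size: a simple illustration.** The protocol states no expected score, spread or stop rate, so there is no figure of its own to reproduce. Everything below is assumed. Let k of five inflations be stopped at a true VAS of s, and let the rest score 20. The mean over all five is (k·s + (5 − k)·20)/5; the mean with the stopped ones unscored is 20.

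- k = 1: (70 + 80)/5 = 30 to (100 + 80)/5 = 36, against 20.
- k = 2: (140 + 60)/5 = 40 to (200 + 60)/5 = 52, against 20.

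The chance that at least one of five first inflations is stopped is 1 − (1 − p)^5, where p is the chance of a stop: 0.41 at p = 0.1, 0.67 at 0.2, 0.83 at 0.3 and 0.92 at 0.4.

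**Size: a model.** First and second inflation VAS are normal with SD 25 and mean 70 − 25·z(1 − p), clipped to 0-100, with correlation 0 to 1 between them. An inflation is stopped at 70 or more, and the second is used only as a retry. A participant's score is the first inflation if it was scored, otherwise the second if that was scored, otherwise missing.

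| p | Mean of all first inflations | Mean if every stopped inflation is unscored | Participants with no stretch score |
|---|---|---|---|
| 0.1 | 38.6 | 33.9-35.0 | 1-10% |
| 0.2 | 49.0 | 40.5-42.0 | 4-20% |
| 0.3 | 56.6 | 44.6-46.3 | 9-30% |
| 0.4 | 62.9 | 47.6-49.4 | 16-40% |

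The third column is an upper bound on the bias from missing scores, because it discards every stopped inflation, including those scored on reaching the diameter. If half of the stopped inflations go unscored, and correlation is 0 to 0.8, the mean at p = 0.2 is 45-47 against 49, with 1-3% of participants lacking a score. If a quarter go unscored, it is 47-48. The model does not cover course 2, where a score exists but was taken too early.

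**The unsettled count.** P(at least 3 of 5) = 10q³(1 − q)² + 5q⁴(1 − q) + q⁵, where q is the chance that a participant counts as a failure. Take p = 0.4 and independent attempts.

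- First attempt decides, q = 0.4: 0.2304 + 0.0768 + 0.0102 = 0.317.
- Both attempts must fail, q = 0.4² = 0.16: 0.0289 + 0.0028 + 0.0001 = 0.032.

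The difference shrinks as the two attempts become more alike and disappears if they always agree.

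**The case against.** The strongest reply is that the score is due on reaching the diameter, not on completing the hold, and that scoring is in real time. That is correct. A reader might infer that primary scores can come only from inflations that were held; the protocol does not support this, because an inflation scored at the diameter and then stopped yields a score.

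A reader might also infer that a missed score is lost for good. Section 6.1 bars completing the scales only once the procedure is over. After a stopped inflation the procedure may still be under way, so a rating at deflation is permitted; it is simply not scheduled.

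Third, one might conclude that participants with the most pain disappear from the result. They do not. Sections 6.1 and 9.1 count those who do not tolerate or do not complete the Coda stage, and section 8.1 lists discomfort or pain as an expected adverse event. Someone who is stopped and declines another attempt has, on a plain reading, not completed the test. The case left open is a stopped first inflation followed by a held second one.

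Other limits also stand. The protocol does not settle whether the second inflation is a retry after severe pain or is given to everyone. Section 3.0 helps only after a wording repair, and ending observation does not in itself say that a score is omitted. The choice between first and highest score is analysis, which a statistical analysis plan may cover. The data collection forms (Appendix A) and Figure 5 are not shown and may hold more detail.

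What survives is the missing time point. Measurement times are fixed in the protocol, and no later analysis can supply a rating that was never taken.

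**Conclusion.** The point holds in a limited form and should be fixed. Carried out exactly as written, section 6.1 gives no scheduled stretch score for an inflation stopped before the diameter. For one stopped during the hold, the score may be too early. The primary pain data can therefore understate discomfort in the direction of the hypothesis.

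The documents do not allow the bias to be sized. Under the assumed model it is at most about 7 to 9 points at a 20% stop rate (49.0 against 40.5-42.0), and about 2 to 4 points if half of the stopped inflations go unscored (49 against 45-47). These figures depend on the assumed SD, the cut at 70 and the retry-only reading. The unsettled status of a held second inflation is a lesser point, but the stopping rule depends on it.

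**What to change.** Add to section 6.1: *If a Coda inflation is stopped for pain, a VAS for the worst pain during that inflation is taken as soon as deflation has begun, before any second attempt and before observation ends, and the fill volume reached is recorded. Scores from stopped inflations are reported with the others.*

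State in sections 6.1 and 9.1, in the same words, whether a stopped first inflation followed by a held second one counts as tolerating the Coda stage. No VAS cut-off is needed, so the decision to rely on the participant's willingness is unchanged.

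The cost is at most one extra short rating per stopped inflation, with no added participants, inflations or inflation time. The rating describes pain that has just ended rather than pain still present, which is a small departure from scoring under stretch.

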7.0 Study Intervention Discontinuation

7.1 Discontinuation of Study Intervention

Participants may withdraw voluntarily from the study, or the PI may discontinue a participant from the study. Discontinuation from study intervention will disqualify participant from further continuation. If a clinically significant finding is identified (including, but not limited to changes from baseline) after enrollment, the investigator or qualified designee will determine if any change in participant management is needed. Any new clinically relevant finding will be reported as an adverse event (AE). Participants will have access to reach the study team should any concerns arise, and a phone call interview will be

scheduled for post procedure day 30 to assess for AEs.

7.2 Participant Discontinuation/Withdrawal

Participants may withdraw voluntarily from the study or discontinue the study intervention at any time.

7.3 Loss to Follow up

A participant will be considered lost to follow-up if he or she fails to return for scheduled visits or is unable to be contacted by the study site staff.

8.0 Adverse Events

8.1 Adverse Events and other reportable events

Any adverse event reported or observed by the participant will be reported per standard IRB reporting. Adverse event means any untoward medical occurrence associated with the use of an intervention in humans, whether or not considered intervention related. Adverse events will be recorded from the time the consent is obtained until the final procedure is complete including completion of VAS and the 30 day follow up phone call. Other reportable information will be reported to the IRB according to standard reporting procedures.

Expected possible adverse events include:

- Damage to the intestinal wall ranging from mild mucosal irritation to full thickness injury or perforation.
- Damage to the stoma
- Bleeding from the intestinal lumen is usually self-limited and will resolve with observation. However, severe damage may require endoscopic or surgical evaluation and/or intervention to obtain hemostasis or repair perforation.
- Discomfort or pain
- Radiation-related risks associated with fluoroscopy include: radiation-induced injuries to the skin and underlying tissues ("burns"), which occur shortly after the exposure, and. radiation-induced cancers

9.0 Statistical Considerations:

9.1 Proposed sample size (number of records to be reviewed):

5 subjects will be enrolled. If 3 fail to complete the radial stretch test with Coda balloon, the study will be terminated.

9.2 Proposed time period to be evaluated

We aim to achieve our enrollment goal within 6 months of approval

9.3 Specify how data will be analyzed and by whom:

Data will be reviewed and analyzed by the study team and departmental statistician

10.0 Supporting Documentation and Operational Considerations:

10.1 Informed Consent Process

Once the study team has been notified of a potential participant, the study team will contact the patient via phone using a phone script (see appendix) or approach the participant in the pre-procedure area at which time the consent will be reviewed, allowing time for any follow up

questions and consideration. Once the participant has agreed to participate, and eligibility has been confirmed and documented including medical history by a study member, the consent process will be completed.

10.2 Study Discontinuation and Closure

At which time the study is complete and all data collection, analysis, and publication, if applicable is complete, the study will be terminated.

10.3 Future Use of Data

We plan to keep this data for future use as this data will contribute to a future project. The data obtained will help to inform future projects and may be included as we further investigate this cohort/disease. Future use of data will be permitted and will be included in the consent.

10.4 Data Handing and Record Keeping

All electronic data will be kept on password protected, encrypted devices within the University of Michigan system which meet current security standards. Any paper records utilized during this review will be kept in a locked cabinet within the Pediatric Surgery research space and/or PI's office. Only study personnel approved by the IRB will have access to study data and records.

Once data collection and analysis is complete, any PHI will be removed from the dataset and data will be maintained for 3 years after the study completion.

11.0 References:

